### Lung Expansion Therapy Devices

Incentive Spirometer

EzPAP® System

► **IF YES, who will generate the randomization scheme?**

- Sponsor
- UVa Statistician.  Answer/Response:
- UVa Investigational Drug Service (IDS)
- Other:  Answer/Response: Study investigators.

## 2. What are the statistical considerations for the protocol?

The objectives section and the statistical section should correspond, and any objective for which analysis is unfeasible should be deleted. Also, the estimates and non-statistical assumptions of the statistical section should be supported by discussion in the background section.

The answer to this question should include:

- Study Design/Endpoints
- Recap of study objectives and endpoint definitions. An assessment of how study objectives will be assessed by identifying & defining which endpoints will be used to assess each component of the study objectives.
- The study design should include contingencies for early stopping, interim analyses, stratification factors (If applicable), and any characteristics to be incorporated in analyses.
- The power/precision of the study to address the major study endpoint(s), the assumptions involved in the determination of power/precision.

--If statistical hypothesis testing is included then specify the null and alternative hypotheses, the test statistic, and the type I and II error rates  
--If precision of an estimate, then provide a definition for precision  
--If other, then specify

**Answer/Response:**

The focus of this study is to use electrical impedance tomography (EIT) monitoring to determine if there is a difference in regional distribution of ventilation when comparing Incentive Spirometry (I.S.) to EzPAP® lung expansion therapy.

Baseline characteristics will be reported as:

- Sex (M/F): n (%)
- Age (years): m (SD)
- Weight (BMI): m (SD) or M (IQR) depending upon normality of data distribution
- Tobacco History: n (%); Never smoked, Current smoker; Former smoker
- Respiratory Related Comorbidities: n (%)

Baseline and post-lung expansion therapy dependent variable metrics will be reported as end-expiratory lung volume impedance (EELI) for each of the following ventilation regions of interest:

- Ventral (Level of measurement- continuous)
- Mid-ventral (Level of measurement- continuous)
- Mid-dorsal (Level of measurement- continuous)
- Dorsal (Level of measurement- continuous)

**3. Provide a justification for the sample size used in this protocol.**

Include the anticipated accrual rate, the accrual goal for the study, including accrual goals by strata if appropriate, adjustments for drop-outs etc. and study duration.

**Answer/Response:** Since this is a proof of concept study, we did not perform a power analysis to determine a sample size.

**4. What is your plan for primary variable analysis?**

Include a sketch of the analysis to assess primary study objectives.

**Answer/Response:**

**PRIMARY NULL HYPOTHESIS:**

There is no difference in regional distribution of ventilation when comparing Incentive Spirometry (I.S.) lung expansion therapy to EzPAP® lung expansion therapy in healthy adult human subjects

**Alternative hypothesis:** There is a difference in regional distribution of ventilation when comparing Incentive Spirometry (I.S.) lung expansion therapy to EzPAP® lung expansion therapy in healthy adult human subjects?

- Independent variable
  - Lung expansion therapy
    1. Incentive Spirometry

2. EzPAP®

- Dependent variables
  - Regional distribution of ventilation areas of interest
    1. Ventral end-expiratory lung volume impedance
    2. Mid-ventral end-expiratory lung volume impedance
    3. Mid-dorsal end-expiratory lung volume impedance
    4. Dorsal end-expiratory lung volume impedance
- Statistical analysis
  - Frequency (n) and percentage (%) will be used to report descriptive categorical level data.
  - Shapiro-Wilk test of normality will be applied to evaluate distribution of continuous level data. Normally distributed data will be presented as mean and standard deviation and 95% confidence interval. Effect size will be reported as Cohen's *d*.
  - Non-normally distributed data will be reported as median and interquartile range. Effect size will be reported as *r*.
  - Independent samples t-test will be applied to normally distributed continuous data to compare group means, and Mann Whitney-U test will be applied to non-normally distributed data.
  - Statistical significance set a  $P$  (2-tailed)  $\leq .0125$  to reduce risk of Type I error.

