### Answer/Response:

Pulmonary function is compromised following upper abdominal surgery. The incidence of post-operative pulmonary complications following upper abdominal surgery ranges between 17% and 88%, and it is a common cause of morbidity and mortality. Physicians order Incentive Spirometry (I.S.) and EzPAP® lung expansion therapy following surgery to encourage improved alveolar ventilation and to reduce risks of post-operative pulmonary complications associated with inhomogeneous distribution of ventilation during deep breathing inspiratory efforts. The primary purpose of this study is to determine if there is a difference in regional distribution of ventilation when comparing resting tidal ventilation with Incentive Spirometry (I.S.) and EzPAP® lung expansion therapy in healthy adult human subjects. We are also interested in determining if regional redistribution of ventilation is time dependent. Lung volume areas of interests include ventral, mid-ventral, mid-dorsal, and dorsal regions. Our null hypotheses is that there is no difference.

A convenience sampling of study participants will be invited to participate in our descriptive observational study. Study participants will be randomly allocated to receive I.S. or EzPAP® therapy after informed consent has been obtained. Electrical Impedance Tomography (EIT) monitoring will be used to visualize and measure regional distribution of ventilation during lung expansion therapy.

EIT lung monitoring and descriptive data will be presented as number (%), mean (SD), or median (IQR) as appropriate. To test our primary hypothesis, the difference between continuous level data will be analyzed with one-way multivariate analysis of variance. This is a proof of concept study that will include 30 human subjects. Statistical significance is set at  $\leq 0.0125$ . We have created a password protected SPSS file (SPSS v.23; Chicago, IL) that will be used for this study's data entry codebook and statistical output generator.

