### 1. Provide target # of subjects (at all sites) needed to complete protocol.

**INSTRUCTIONS:** If this is NOT a database protocol, this number should be the same as the number of subjects needed to obtain statistically significant results.

**Answer/Response:** 30. This is a proof of concept study. No power analysis was performed.

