**Answer/Response:**

While participants will not benefit directly from this study, we anticipate that important information will be gained from our EIT monitoring of regional distribution of ventilation. Future patients may benefit from our study findings as we hope to advance clinical understandings associated with these

IRB-HSR # 19661: A descriptive observational pilot study comparing regional distribution of ventilation during lung expansion therapy in healthy human subjects

therapies with use of EIT monitoring. Our findings also have potential to reduce the use of clinically ineffective lung expansion therapy, which has potential for more appropriate utilization of health care resources, benefitting society in general.

The potential benefit for study participants will not be realized directly since our aim is to monitor regional distribution of ventilation in response to I.S. or EzPAP® lung expansion therapy. These therapies are considered to be standards of care in post-operative surgical patients. Loss of dorsal regional lung volume (i.e., atelectasis) is an example of a post-operative pulmonary complication. EzPAP® is a lung expansion therapy that is used as an alternative to I.S. lung expansion therapy for increasing dorsal regional lung volume (i.e., functional residual capacity) in an effort to prevent or reverse atelectasis. When expiratory positive airway pressures of 5, 10, and 15 cmH2O was administered to a small group of healthy human subjects, Garrard et al. (Chest, 1978) found a positive pressure of 15 cmH2O was associated with the greatest FRC increase when compared to zero pressure and baseline FRC measurements. We are unable to identify previous research describing whether regional redistribution of ventilation is sustained after completing I.S. or EzPAP lung expansion therapy.

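### The primary tests compare regional EELI levels, so they cannot separate an overall end-expiratory volume difference from the redistribution that the hypothesis is about

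*Combined protocol and SAP*

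**What the plan says.** All references are to the combined protocol and SAP.

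- **Hypothesis.** Statistical Considerations, item 4 (primary variable analysis), states the alternative as: "There is a difference in regional distribution of ventilation when comparing Incentive Spirometry (I.S.) lung expansion therapy to EzPAP® lung expansion therapy".
- **Endpoint.** Item 2 of the same section: "Baseline and post-lung expansion therapy dependent variable metrics will be reported as end-expiratory lung volume impedance (EELI) for each of the following ventilation regions". Item 4 lists the same four values (ventral, mid-ventral, mid-dorsal, dorsal) as the dependent variables. No unit or normalisation is given.
- **Test.** Item 4: "Independent samples t-test will be applied to normally distributed continuous data to compare group means, and Mann Whitney-U test will be applied" to data that are not normal. The two-tailed threshold is .0125.
- **A different test in the Brief Summary/Abstract.** There, "the difference between continuous level data will be analyzed with one-way multivariate analysis of variance", also with significance at 0.0125.
- **Secondary analysis.** Item 5 refers back to item 4, although the secondary question is also about redistribution.
- **Rationale.** Risk/Benefit Analysis, item 1, says that EzPAP is used to raise dorsal lung volume, which it equates with functional residual capacity (FRC). It cites a small study in healthy subjects in which the highest expiratory pressure "was associated with the greatest FRC increase when compared to zero pressure and baseline FRC measurements".
- **Size.** Human Participants, item 1: "30. This is a proof of concept study. No power analysis was performed".

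**The concern.** Distribution is a relation among regions: how much of the signal lies in the ventral, middle and dorsal lung. A comparison of one region's level between arms says nothing about that relation, and four such comparisons side by side still do not. MANOVA on the four levels asks whether any of the four means differs, which is also true when all four move together. The plan has no endpoint that relates one region to another, and no rule for turning four P values into one conclusion about distribution.

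The competing explanation is foreseeable. The endpoint is an end-expiratory quantity, and the plan itself cites a rise in FRC, a whole-lung end-expiratory volume, with expiratory positive pressure. If EzPAP raises overall end-expiratory volume more than incentive spirometry does, a significant result could be reported as redistribution when the regional pattern has not changed. Real redistribution may also be missed, because separate t-tests leave the between-subject variation that is common to all regions in the error term.

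**Working it through.** **Inputs.** From the plan: 30 subjects, no dropout expected, four regions, 0.0125 two-tailed. Assumed, because the plan does not give them: 1:1 allocation (n = 15 per arm), normal data with equal SDs, equal correlation ρ between regions (0, 0.5, 0.8), and the effect sizes.

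**The plan's threshold.** 0.05 / 4 = 0.0125. The plan does not state this derivation, but it matches one test per region.

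**Case A: an equal rise of d SD in all four regions, no redistribution.**

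*Separate t-tests.* The noncentrality is d√(n/2). For d = 0.8 this is 0.8 × √7.5 = 2.19, and power in one region at 0.0125 is 0.334. With ρ = 0, P(at least one region) = 1 − (1 − 0.334)⁴ = 0.80. For d = 0.5, single-region power is 0.115 and 1 − 0.885⁴ = 0.39, within a point of the simulated 38%. Simulation (at least 20,000 trials per cell) supplies the correlated cases.

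*MANOVA (Hotelling's T² on four levels).* λ = (n/2)·4d²/(1 + 3ρ), with F on 4 and 25 df. For d = 0.8: λ = 7.5 × 2.56/(1 + 3ρ) = 19.2, 7.68 and 5.65.

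*Contrast test (T² on three between-region differences).* An equal shift makes every contrast zero, so λ = 0 and the test rejects at its nominal rate.

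| Equal rise, chance of rejection | ρ = 0 | ρ = 0.5 | ρ = 0.8 |
|---|---|---|---|
| 0.5 SD, any region at 0.0125 | 38% | 30% | 22% |
| 0.8 SD, any region at 0.0125 | 80% | 64% | 53% |
| 0.8 SD, all four regions at 0.0125 | 1% | 8% | 17% |
| 0.8 SD, MANOVA at 0.0125 | 76% | 27% | 18% |
| 0.8 SD, contrast test at 0.05 | 5% | 5% | 5% |

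Simulated entries move by up to about a point between runs. With no shift at all, the any-region rate is 3% to 5%. The first three rows show a further trap: a purely global effect, when detected, usually appears in some regions and not others, which looks like redistribution.

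**Case B: real redistribution, −0.7 SD ventral and +0.7 SD dorsal.** The shifts sum to zero, so λ = (n/2)·(0.49 + 0.49)/(1 − ρ) = 7.35, 14.7 and 36.75 for both multivariate tests. The contrast test spends 3 numerator df where MANOVA spends 4.

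| Power | ρ = 0 | ρ = 0.5 | ρ = 0.8 |
|---|---|---|---|
| Any region at 0.0125 | 44% | 47% | 48% |
| Contrast test at 0.05 | 54% | 86% | 99.9% |
| MANOVA at 0.05 | 48% | 81% | 99.7% |

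**Case C: a proportional rise, shares unchanged.** Assumed regional levels in the ratio 15/35/35/15, log-SD 0.25, ρ from 0.3 to 0.8. The contrast test on raw levels at 0.05 rejects in 38% to 50% of trials for a 30% rise and in 76% to 89% for a 50% rise. On log levels, or on three of the four shares, it stays at about 5%. The measurement scale is therefore part of the remedy.

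**The case against.** - **The rationale is regional.** A reader might infer that the plan predicts an equal rise in all four regions under EzPAP. It does not. It names dorsal volume, and it reports the cited FRC rise without a regional breakdown. A mainly dorsal rise would itself be redistribution, and rejection would then be right. What stands is that an overall rise is foreseeable and the tests cannot tell the two apart.
- **Nothing says that a global rise will be declared redistribution.** The plan has no decision rule, and every rate above rests on assumed effects; at 0.5 SD the any-region rate is 22% to 38%. The point is a risk whose size depends on the effect, not a certainty.
- **MANOVA is not inefficient.** This is correct: it uses the between-region covariance and comes close to the contrast test at the same alpha. The loss of power belongs to the separate t-tests. MANOVA's fault is that it also responds to a global shift.
- **EELI might be meant as a share.** The problem would then largely vanish. The plan does not say so. The percentage-of-global measure in its monitoring section is regional tidal variation, listed as a screen display and not as an endpoint; the same section speaks of recording end-expiratory impedance changes.
- **It is a 30-subject proof-of-concept study, and regional summaries will be reported.** A reader could notice parallel shifts in the means. That status excuses limited power, but not a formal test of a different hypothesis.

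**Conclusion.** The mismatch is real. The stated hypothesis concerns distribution, whereas both the separate tests and the abstract's MANOVA concern levels. Under an equal 0.8 SD rise with no redistribution, the separate tests flag at least one region in about half to four-fifths of trials, and MANOVA at the documented 0.0125 rejects in about a fifth to three-quarters. A contrast test holds 5%.

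These sizes rest on 15 per arm, normality, equal correlations and effect sizes that the plan does not supply, and on EELI being a level or a change in level. That the planned tests respond to a common shift does not depend on those figures. The documents do not support the stronger inference that the plan expects a uniform rise or is bound to misreport one. This should be corrected before analysis.

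**What to change.** 1. In Statistical Considerations, items 2 and 4, state the unit and normalisation of EELI, and define the distribution endpoint on a relative scale: each region's share of the global signal, or log regional levels if the values are strictly positive.
2. Test it once between arms at 0.05, with Hotelling's T² on three of the four shares, or the arm-by-region interaction on the log scale. One test does not need the 0.0125 threshold.
3. Follow with Holm-adjusted regional comparisons on the same scale.
4. Report the global change separately, as a volume effect.
5. Do not run the interaction on raw levels unless an additive effect is justified; Case C shows why.
6. Bring the Brief Summary/Abstract into line with item 4, so that one primary test is named.

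**Cost.** This is a change of wording and a standard repeated-measures or multivariate procedure. It needs no new subjects or measurements. The downsides are that differences in regional levels become descriptive, and that shares are unstable (and logs unusable) if EELI is recorded as a change that can be near zero or negative. Step 1 therefore has to come first.

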**PRIMARY RESEARCH QUESTION:**

**Is there a difference in regional redistribution of ventilation when comparing eupneic tidal ventilation during Incentive Spirometry (I.S.) or EzPAP® lung expansion therapy in healthy adult human subjects?**

**Null hypothesis:** There is no difference in regional redistribution of ventilation when comparing eupneic tidal ventilation during Incentive Spirometry (I.S.) or EzPAP® lung expansion therapy in healthy adult human subjects?

**Alternative hypothesis:** There is a difference in regional redistribution of ventilation when comparing eupneic tidal ventilation during Incentive Spirometry (I.S.) or EzPAP® lung expansion therapy in healthy adult human subjects?

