**SECONDARY RESEARCH QUESTIONS:**

**1. Is there a difference in regional redistribution of ventilation measured immediately after lung expansion therapy when compared to regional distribution of ventilation measured 5-minutes after lung expansion therapy?**

**Null hypothesis:** There is no difference in regional redistribution of ventilation measured immediately after lung expansion therapy when compared to regional distribution of ventilation measured 5-minutes after lung expansion therapy?

**Alternative hypothesis:** There is no difference in regional redistribution of ventilation measured immediately after lung expansion therapy when compared to regional distribution of ventilation measured 5-minutes after lung expansion therapy?

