- EIT device calibration and signal check
  - Researcher will initiate a PulmoVista 500 EIT monitoring device calibration each day prior to performing new study participant EELI measurements.
  - A skin-electrode signal check will be performed to ensure that a minimum of 15 of 16 electrodes have sufficient contact with the participant's skin surface and signal quality is stable. Researchers will use the following status display and explanation to determine adequacy of electrode contact and signal quality.

Status	Explanation
Gray	Skin-electrode contact is sufficient for measurement to proceed
White	Skin-electrode contact is unstable, measurement will proceed but signal quality may be impaired
Red	Skin-electrode contact is insufficient for measurement to proceed

• M

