**REGIONAL DISTRIBUTION OF VENTILATION MONITORING:**

- PulmoVista monitoring and lung expansion therapy will occur only one time as described above. .
- The following information will be displayed on the PulmoVista 500 device’s main monitoring screen during lung expansion therapy, but study investigator staff administering therapy and study participants will be blinded from information displayed on the screen’s monitor during therapy session in an effort to reduce performance bias:

[figure not shown]
A: Dynamic imaging showing impedance changes in a caudo-cranial image referenced to a dynamic baseline.  
 B: Tidal image showing EELI during inspiration and exhalation of the last detected breath.  
 C: Global impedance waveform showing relative impedance changes across electrode plane.  
 D: Regional impedance waveforms  
 F: Tidal respiratory rate  
 G: Global tidal variation displayed as 100%.  
 H: Regional tidal variation displayed as a percentage of global tidal variation.  
 - Once lung expansion therapy

IRB-HSR # 19661: A descriptive observational pilot study comparing regional distribution of ventilation during lung expansion therapy in healthy human subjects

session has ended, the researcher will detach trunk cables from electrode cables, detach reference electrode snap from adhesive ECG electrode, unclamp the electrode belt, and then remove belt from the study subject. Subject participation in this study is considered complete at this time.

- Inspect of electrode belt contact area will be performed to assess for evidence of skin irritation or bruising. Study participant will be notified by study investigator at the time of skin assessment if significant skin irritation or bruising is present. Finding will be recorded by study investigator.

- Displaying changes
  - The following information will be displayed and used to record pre and post lung expansion therapy end-expiratory lung impedance changes:

- Electrode belt, patient cable, and PulmoVista 500 EIT device (Draeger; Lubeck, Germany) will be removed study participant’s room and returned to a storage location outside of patient care areas.
- Following each EIT to subject interface disconnect, an alcohol, aldehyde, or quaternary ammonium based compound will be soaked on a wipe cloth to disinfect the surfaces of the patient cable, electrode belt, trunk cable, and EIT unit.

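### The primary hypothesis is worded as regional distribution of ventilation, but every EIT variable named for analysis is regional end-expiratory lung impedance (EELI), and nothing in the plan connects the two

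*Combined protocol and SAP*

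**What the plan says.** Statistical Considerations, item 4 (primary variable analysis), states the primary null as "There is no difference in regional distribution of ventilation when comparing Incentive Spirometry (I.S.) lung expansion therapy to EzPAP® lung expansion therapy". The dependent variables that follow are four regional impedances: "Ventral end-expiratory lung volume impedance" and its mid-ventral, mid-dorsal and dorsal counterparts. Item 2 of the same section names the same metric for baseline and post-therapy reporting. Item 5 (secondary analysis) only refers back to item 4.

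The Hypothesis to be Tested section is also worded in terms of ventilation. Its primary question is "Is there a difference in regional redistribution of ventilation when comparing eupneic tidal ventilation during Incentive Spirometry (I.S.) or EzPAP® lung expansion therapy", and its secondary question concerns "regional redistribution of ventilation measured immediately after lung expansion therapy when compared to regional distribution of ventilation measured 5-minutes after lung expansion therapy". The Brief Summary and the opening of the Hypothesis section likewise say that EIT will measure regional distribution of ventilation.

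In Biomedical Research, item 1, the calibration step is to be done "prior to performing new study participant EELI measurements". Under Regional Distribution of Ventilation Monitoring, the list of screen contents includes, as item H, "Regional tidal variation displayed as a percentage of global tidal variation". Item B of that list describes the tidal image as one that shows EELI. The later paragraph on displaying changes says that the display is used to record end-expiratory impedance changes before and after therapy.

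**The concern.** Distribution of ventilation is ordinarily understood as how each breath is divided between regions. EELI, by the name the plan gives it, is where a region sits when the breath is over. A region can hold more air at end-expiration without receiving a larger share of the breath, and the reverse is also possible.

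If the analysis follows item 4 literally, a difference between arms in end-expiratory volume would be written up as a difference in distribution of ventilation. A shift in distribution with unchanged EELI would be written up as no difference. What is at stake is the meaning of the trial's main conclusion. Its conduct and safety are not affected.

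**Working it through.** There is no figure in the plan to reproduce: no power calculation, standard deviation or expected difference is given for any EIT quantity. The check is therefore a comparison of sections, followed by simple arithmetic.

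**Step 1. What the hypotheses are about.** The Brief Summary, the Hypothesis to be Tested section and item 4 of Statistical Considerations all name regional distribution, or redistribution, of ventilation.

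**Step 2. What is analysed.** Item 4 names four dependent variables.
- On regional EELI: 4 of 4.
- On regional tidal share: 0 of 4.

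Item 2 names EELI only, and item 5 adds nothing.

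**Step 3. Is there a bridge?** I looked for a justification, a ratio, a regional share or any rule that turns EELI into a distribution measure. None of the sections that name an EIT quantity gives one.

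**Step 4. Is a direct measure available?** Display item H expresses regional tidal variation as a percentage of the global value. That is a distribution measure. It appears only as screen content, and no readable section makes it an outcome. The screen figure and the list under displaying changes are missing from the text available to me, so I claim no more than that. The sentence introducing that list names end-expiratory changes.

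**Step 5. Can the two measures disagree?** These units are assumed and are not trial data. Let share in a region = 100 × regional amplitude ÷ sum of the four amplitudes, and let EELI be the end-expiratory level.

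| Case | Amplitudes, arm 1 | Amplitudes, arm 2 | Level difference per region | EELI difference | Share difference (points) |
|---|---|---|---|---|---|
| (i) | 20/30/30/20 | 20/30/30/20 | 10 | 10/10/10/10 | 0/0/0/0 |
| (ii) | 20/30/30/20 | 10/25/35/30 | 0 | 0/0/0/0 | −10/−5/+5/+10 |

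In each arm the amplitudes sum to 100, so the shares equal the amplitudes. The tests in item 4 would see case (i) and be blind to case (ii). This holds by construction, because a level and an amplitude are different numbers. It shows that the measures can part company, not that they will do so here.

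**Step 6. The significance threshold.** 4 × 0.0125 = 0.05, which fits one test per region. The plan states neither the 0.05 nor the division, so this reading is my inference. It matters only for keeping one set of four tests as primary in the fix.

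**The case against.** The best defence is that item 4 supplies its own operational definition. The four EELI variables sit under a heading that labels them as areas of interest for distribution of ventilation, so a reader knows what will be tested. The rationale also leans towards lung volume. The Brief Summary speaks of lung volume areas, the Background asks whether redistribution of lung volume depends on time, and Risk/Benefit Analysis, item 1, equates dorsal regional lung volume with functional residual capacity. On this view the investigators mean regional lung volume throughout, and only the wording is loose. A further defence is that EELI may be used loosely for a tidal quantity, since display item B attaches that label to a tidal image. The analysis might then match the hypothesis, with only the label wrong.

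Much of this stands. It rules out two stronger readings that a reader might infer. One is that the primary hypothesis has no defined outcome; the heading in item 4 gives it one, loosely. The other is that an EELI result can say nothing about the hypothesis on any reading. That requires fixing distribution of ventilation as the share of each breath, which no section does explicitly. Nor does the phrase about eupneic tidal ventilation in the primary question prove that a tidal outcome was intended; it may simply name the resting state used for comparison.

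What does not stand is leaving the text alone. The heading labels regions and gives no reason for the substitution. If the investigators mean lung volume, the hypotheses should say so; if they mean a tidal quantity, the outcome is mislabelled. The form itself instructs that "The objectives section and the statistical section should correspond, and any objective for which analysis is unfeasible should be deleted".

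**Conclusion.** The concern holds in a limited form. The hypotheses are worded as distribution of ventilation, all four named variables are EELI, no section links the two, and the distribution measure on the device screen is assigned to no analysis in the readable text. Taken literally, the plan could attach a ventilation conclusion to a lung-volume result, or overlook a shift in ventilation at equal EELI.

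These consequences rest on EELI meaning the end-expiratory level, as its name says. If it is used for a tidal quantity, the fault reduces to a wrong label on the primary outcome. The wording needs correcting either way.

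Neither size nor likelihood can be stated, because the documents give no EELI or tidal-variation values. A reader might infer that a false conclusion is probable because Risk/Benefit Analysis, item 1, cites a rise in functional residual capacity under expiratory positive pressure. That passage does not show that the effect outlasts therapy or differs between these two arms, so it does not support the inference. This should be settled before analysis.

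**What to change.** Define EELI once and reconcile display item B with that definition. Then take one of two routes.

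- **(a) Reword.** State the hypotheses in the Hypothesis to be Tested section and in item 4 of Statistical Considerations as regional end-expiratory lung volume, and limit the conclusions to that. The cost is wording only, but the trial then makes no claim about distribution of ventilation.
- **(b) Keep the ventilation hypothesis.** Make regional tidal variation as a percentage of global (display item H) its outcome in the four regions, taken from the recordings already planned, in one prespecified window. Choose the window only after the comparisons are reconciled: the Background and Hypothesis sections compare resting breathing with therapy and early with later post-therapy readings, while item 4 compares the two devices. Name one set of four regional tests as primary at 0.0125 and label EELI secondary, or keep EELI primary and make the distribution claim secondary.

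Route (b) costs one more parameter to extract. If the window falls during therapy, the report must also note that the Incentive Spirometry procedure uses deep breaths and the EzPAP procedure normal breaths, so shares would be compared at different breath depths. Neither route adds participants or visits.
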